## 11. Tertiary Endpoint Descriptions

### 11.1 – Tertiary Endpoint #1

Endpoint Description: Time to death through 24 weeks, using the pre-COVID-19 population.

Response Variable Definition: Deaths occurring from the time of randomization through the Week 24 assessment. In the event the patient did not have complete follow-up through Week 24, the patient will be censored at the time of their last follow-up prior to the Week 24 assessment.

Additional Covariates in Addition to Randomized Treatment: atrial fibrillation status at time of randomization

Handling of Dropouts and Missing Data: Each patient will be evaluated based on the available follow-up. No adjustment for incomplete follow-up will be made.

Sensitivity Analysis: Re-calculate the endpoint analysis using the original ITT population.

Statistical Tests: The Cox regression model for survival data (PROC PHREG in SAS) will be used to test the statistical significance of differences in time to death between the treatments. Kaplan-Meier curves will be generated to graphically display the event rates as a function of time from randomization in each treatment.

Interpretation of Results: A lower rate of death through 24 weeks indicates lower mortality in the LCZ696 arm versus Valsartan.

## 11.2 – Tertiary Endpoint #2

Endpoint Description: Time to cardiovascular death through 24 weeks, using the pre-COVID-19 population.

Response Variable Definition: Site-classified cardiovascular deaths occurring from the time of randomization through the Week 24 assessment. In the event the patient did not have complete follow-up through Week 24, the patient will be censored at the time of their last follow-up prior to the Week 24 assessment.

Additional Covariates in Addition to Randomized Treatment: atrial fibrillation status at time of randomization

Handling of Dropouts and Missing Data: Each patient will be evaluated based on the available follow-up. No adjustment for incomplete follow-up will be made.

Sensitivity Analysis: Re-calculate the endpoint analysis using the original ITT population.

Statistical Tests: The Cox regression model for survival data (PROC PHREG in SAS) will be used to test the statistical significance of differences in time to cardiovascular death between the treatments. Kaplan-Meier curves will be generated to graphically display the event rates as a function of time from randomization in each treatment.

Interpretation of Results: A lower rate of cardiovascular death through 24 weeks indicates lower cardiovascular-related mortality in the LCZ696 arm versus Valsartan.

### **11.3 – Tertiary Endpoint #3**

Endpoint Description: Time to first unplanned heart failure hospitalization through 24 weeks, using the pre-COVID-19 population.

Response Variable Definition: Unplanned heart failure hospitalizations occurring from the time of randomization through the Week 24 assessment. The event time will be set at the time of the first unplanned heart failure hospitalization. In the event the patient did not have complete follow-up through Week 24, the patient will be censored at the time of their last follow-up prior to the Week 24 assessment.

Additional Covariates in Addition to Randomized Treatment: atrial fibrillation status at time of randomization

Handling of Dropouts and Missing Data: Each patient will be evaluated based on the available follow-up. No adjustment for incomplete follow-up will be made.

Sensitivity Analysis: Re-calculate the endpoint analysis using the original ITT population.

Statistical Tests: The Cox regression model for survival data (PROC PHREG in SAS) will be used to test the statistical significance of differences in time to first unplanned heart failure hospitalization between the treatments. Kaplan-Meier curves will be generated to graphically display the event rates as a function of time from randomization in each treatment.

Interpretation of Results: A lower rate of unplanned heart failure hospitalizations through 24 weeks indicates lower heart failure hospital admission rates in the LCZ696 arm versus Valsartan.

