16.5 Analysis of Secondary, Tertiary and Exploratory Endpoints

The key secondary endpoint, *days alive and out of hospital at 6 months, not listed for transplant (status 1A, 1B or 1-4) or undergoing transplant, implanted with an LVAD, maintained or started on continuous inotropic therapy for ≥ 7 days, or has had two hospital admissions for HF (other than the index admission*)*, will be analyzed using a regression model with indicator variables for the treatment assignment and atrial fibrillation at enrollment. For time-to-event endpoints, the

Cox regression model for survival data will be used to test the statistical significance of differences in mortality between the treatments. Kaplan-Meier curves will be generated to graphically display the mortality rates as a function of time from randomization in each treatment. Continuous endpoint data will be modelled using general linear models. Mixed models will be used for the analysis of longitudinal data. The unmatched win ratio approach of Pocock et al. will be used to analyze the modified composite endpoints.¹¹

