### **11.5 – Tertiary Endpoint #5**

Endpoint Description: Time to cardiovascular death or first unplanned heart failure hospitalization through 24 weeks, using the pre-COVID-19 population.

Response Variable Definition: Site-classified cardiovascular death or unplanned heart failure hospitalizations occurring from the time of randomization through the Week 24 assessment. The event time will be set at the time of the earliest of cardiovascular death or first unplanned heart failure hospitalization. In the event the patient did not have complete follow-up through Week 24, the patient will be censored at the time of their last follow-up prior to the Week 24 assessment.

Additional Covariates in Addition to Randomized Treatment: atrial fibrillation status at time of randomization

Handling of Dropouts and Missing Data: Each patient will be evaluated based on the available follow-up. No adjustment for incomplete follow-up will be made.

Sensitivity Analysis: Re-calculate the endpoint analysis using the original ITT population.

Statistical Tests: The Cox regression model for survival data (PROC PHREG in SAS) will be used to test the statistical significance of differences in time to cardiovascular death or first unplanned heart failure hospitalization between the treatments. Kaplan-Meier curves will be generated to graphically display the event rates as a function of time from randomization in each treatment.

Interpretation of Results: A lower rate of unplanned heart failure hospitalizations or cardiovascular death through 24 weeks indicates lower clinical event rates in the LCZ696 arm versus Valsartan.

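### Kaplan-Meier curves for first HF hospitalisation (Tertiary #3) will modestly overstate the 24-week event rates if competing deaths are censored, as the SAP implies

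*SAP*

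**What the plan says.** SAP 11.3 (Tertiary #3) analyses time to first unplanned HF hospitalisation with a Cox model and adds a graphical display: "Kaplan-Meier curves will be generated to graphically display the event rates as a function of time from randomization in each treatment". The event is the hospitalisation only: "The event time will be set at the time of the first unplanned heart failure hospitalization". For a patient without complete follow-up to week 24, "the patient will be censored at the time of their last follow-up prior to the Week 24 assessment", and "No adjustment for incomplete follow-up will be made". The section does not say how a patient who dies without an HF hospitalisation is coded.

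SAP 11.2 (Tertiary #2) covers "Site-classified cardiovascular deaths occurring from the time of randomization through the Week 24 assessment" and plans the same display: "Kaplan-Meier curves will be generated to graphically display the event rates". SAP 11.5 (Tertiary #5) uses the composite in which "The event time will be set at the time of the earliest of cardiovascular death or first unplanned heart failure hospitalization". In both, non-cardiovascular death is not an event, and the censoring rule is the same.

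Protocol 16.5 names the method more narrowly: "Kaplan-Meier curves will be generated to graphically display the mortality rates as a function of time from randomization in each treatment". The SAP carries that sentence over to every time-to-event endpoint. Neither document mentions competing risks or cumulative incidence.

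**The concern.** Kaplan-Meier treats a censored patient as someone who could still have the event later. A patient who has died cannot be hospitalised later. If such deaths are censored, one minus Kaplan-Meier describes a hypothetical setting in which nobody dies first, not the share of randomised patients who are hospitalised. It can equal that share or exceed it, never fall below it.

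The SAP wants these curves to show event rates by arm, and readers will take the week-24 value as the observed risk. In a class IV population deaths before hospitalisation will not be rare, so the rates shown would be somewhat too high. The gap between the arms can also move, because the overstatement depends on each arm's hospitalisation and death rates. The same sentence is sound in SAP 11.1 (all-cause death) and 11.4 (death or HF hospitalisation), where no death lies outside the endpoint.

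**Working it through.** **The plan's own event-rate figure.** Protocol 16.2 anticipates 40% with death or first HF re-admission at 24 weeks on valsartan. It states 88% power against 25% and 55% against 30%, with 400 patients and two-sided alpha 0.05. With 200 per arm and the normal approximation:

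- 40% vs 25%: pooled SE = √(2 × 0.325 × 0.675 / 200) = 0.0468; unpooled SE = √((0.24 + 0.1875) / 200) = 0.0462; z = (0.15 − 1.96 × 0.0468) / 0.0462 = 1.26; power 89.6%.
- 40% vs 30%: the same steps give 55.5%.

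Both agree with the protocol to within 2 points. This confirms only how the composite rates were used. It says nothing about the size of the Kaplan-Meier bias.

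**Inputs for the bias.**

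- C, the 24-week risk of death or first HF hospitalisation: 40% and 25%, from Protocol 16.2.
- d, the share who die before any HF hospitalisation: not in the documents. Assumed 2% to 15%.
- Constant cause-specific hazards over 24 weeks: assumed.

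**Formulas for Tertiary #3.** True cumulative incidence = C − d. One minus Kaplan-Meier with deaths censored = 1 − (1 − C)^(1 − d/C).

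Example with C = 40%, d = 10%: true incidence 30.0%; one minus Kaplan-Meier = 1 − 0.6^0.75 = 31.83%.

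| C | d (assumed) | True incidence | 1 − KM | Overstatement (points) |
|---|---|---|---|---|
| 40% | 2% | 38.0% | 38.45% | 0.45 |
| 40% | 5% | 35.0% | 36.04% | 1.04 |
| 40% | 10% | 30.0% | 31.83% | 1.83 |
| 40% | 15% | 25.0% | 27.33% | 2.33 |
| 25% | 2% | 23.0% | 23.25% | 0.25 |
| 25% | 5% | 20.0% | 20.56% | 0.56 |
| 25% | 10% | 15.0% | 15.85% | 0.85 |
| 25% | 15% | 10.0% | 10.87% | 0.87 |

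A simulation of 400,000 patients at C = 40%, d = 10% gave 31.8% against 30.0%, as the formula predicts.

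**Difference between arms.** Take C = 40%, d = 10% on valsartan and C = 25%, d = 5% on LCZ696. The true gap is 30.0 − 20.0 = 10.0 points. The displayed gap is 31.83 − 20.56 = 11.27 points, a shift of about 1.3. With d = 10% in both arms the shift is 1.83 − 0.85 = 0.98 points. Over all pairings in the table it runs from 0.45 − 0.87 = −0.42 to 2.33 − 0.25 = +2.08 points.

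**Tertiary #2 (CV death).** With total death risk D and non-cardiovascular share s, both assumed, true incidence = D(1 − s) and one minus Kaplan-Meier = 1 − (1 − D)^(1 − s). For D of 5% to 20% and s of 5% to 30%, the overstatement is 0.01 to 0.46 points; the top value is 14.46% against 14.0%.

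**Tertiary #5 (CV death or HF hospitalisation).** Take C = 40% and assume non-cardiovascular death comes first in 0.5% to 3%. The overstatement runs from 0.12 points (39.62% vs 39.5%) to 0.66 points (37.66% vs 37.0%).

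**The case against.** The strongest reply is that this changes little:

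- The curves are descriptive displays for tertiary endpoints. The plan also shows all-cause death (11.1) and death or HF hospitalisation (11.4) by curves free of the problem, and death ranks first in the win ratio (12.1).
- The analysis population is 335 patients (SAP 3), about 167 per arm. A 30% rate then has a 95% interval of about ±1.96 × √(0.3 × 0.7 / 167) = ±7 points, so a bias of 1 to 2 points is unlikely to alter a reading.
- The censored Kaplan-Meier curve is the natural companion of a cause-specific Cox model, so discarding it is partly a matter of preference.

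All of this stands. It limits the weight of the point and argues for adding a curve rather than insisting on removal. It does not make the displayed rate correct.

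Three stronger readings might be inferred, and the documents support none of them:

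- *The Cox tests are compromised.* They are not. Censoring competing deaths gives a valid comparison of cause-specific hazards.
- *The overstatement reaches 3 points or more.* A reader might take 40% as the HF-hospitalisation rate alone and combine it with 8% to 18% mortality, which gives 1.5 to 3.4 points. The protocol's 40% already includes death. That combination implies a composite of 1 − 0.6 × 0.92 = 44.8% to 1 − 0.6 × 0.82 = 50.8%, above the planning figure.
- *The SAP states that deaths are censored.* It does not. Censoring follows from the general incomplete-follow-up rule and the absence of any other handling.

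**Conclusion.** The point holds as a minor one, centred on Tertiary #3. If SAP 11.3 is followed as written, with deaths before HF hospitalisation censored, the displayed 24-week rates will overstate the incidence. The direction is certain under that coding; the size is not. It rests on the protocol's composite rates, constant hazards, and an assumed 2% to 15% dying before any HF hospitalisation. On that basis it is about 0.3 to 2.3 points per arm, with a shift of about 1 point in the displayed difference under plausible splits. The top of the range needs 15% of patients to die before any HF hospitalisation. For Tertiary #2 and #5 the effect is close to negligible, and they should not carry the same weight. No hypothesis test changes.

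**What to change.** - In SAP 11.3, and for consistency in 11.2 and 11.5, display and report 24-week rates from Aalen-Johansen cumulative incidence curves, with the competing death as its own event type: any death for #3, non-cardiovascular death for #2 and #5.
- State in each section how those deaths are coded.
- Keep the Cox models and label their hazard ratios as cause-specific. A Kaplan-Meier curve may stay as a companion to the model if its caption says that competing deaths are censored.
- Leave Kaplan-Meier unchanged for Tertiary #1 and #4.

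The cost is a few SAP sentences and a standard option in the same SAS procedures. No new data are needed. The reported rates will be slightly lower. Because cumulative incidence also depends on the hazard of competing death, the separation of the new curves need not match the cause-specific hazard ratio, and the report should say so.

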#### **11.4 – Tertiary Endpoint #4**

Endpoint Description: Time to death or first unplanned heart failure hospitalization through 24 weeks, using the pre-COVID-19 population.

Response Variable Definition: Death or unplanned heart failure hospitalizations occurring from the time of randomization through the Week 24 assessment. The event time will be set at the time of the earliest of death or first unplanned heart failure hospitalization. In the event the patient did not have complete follow-up through Week 24, the patient will be censored at the time of their last follow-up prior to the Week 24 assessment.

Additional Covariates in Addition to Randomized Treatment: atrial fibrillation status at time of randomization

Handling of Dropouts and Missing Data: Each patient will be evaluated based on the available follow-up. No adjustment for incomplete follow-up will be made.

Sensitivity Analysis: Re-calculate the endpoint analysis using the original ITT population.

Statistical Tests: The Cox regression model for survival data (PROC PHREG in SAS) will be used to test the statistical significance of differences in time to death or first unplanned heart failure hospitalization between the treatments. Kaplan-Meier curves will be generated to graphically display the event rates as a function of time from randomization in each treatment.

Interpretation of Results: A lower rate of unplanned heart failure hospitalizations or death through 24 weeks indicates lower clinical event rates in the LCZ696 arm versus Valsartan.

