3 EXECUTIVE SUMMARY

Title	Entresto™ (LCZ696) In Advanced Heart Failure (LIFE Study)
Indication	New York Heart Association (NYHA) Class IV heart failure with a reduced ejection fraction (EF ≤ 35%).
Location	Approximately 40 clinical centers in the United States
Brief Rationale	
Patients with advanced heart failure with reduced ejection fraction (HFrEF) have extremely high morbidity and mortality with 1 year outcomes of death and hospitalization of approximately 50%.^{1,2} For the most advanced heart failure patients, the evidence base for medical treatment is limited with consensus guidelines recommending consideration for either cardiac transplant or ventricular assist device, or palliative care.³
 
The PARADIGM-HF trial showed that LCZ696, which consists of the neprilysin inhibitor sacubitril and the ARB valsartan, improved morbidity and mortality in patients with chronic HFrEF in comparison to enalapril.¹ However, limited experience with advanced heart failure patients was gained from patients enrolled in the trial. Additionally, experience is needed on the use of, and outcomes with, LCZ696 in patients unable to tolerate target doses of ACEI/ARB compared to reduced doses of LCZ696.
 
Hypothesis: In patients with symptomatic heart failure due to left ventricular systolic dysfunction, treatment with LCZ696 for 24 weeks will improve NT-proBNP levels, which reflect hemodynamic and clinical status, compared to treatment with valsartan.

Study Design	This study will be a randomized, double-blinded trial of advanced heart failure subjects with 1:1 randomization to either LCZ696 (sacubitril and valsartan) or valsartan. Study drug will be administered in a double-dummy fashion, in which subjects take active (LCZ696 or valsartan) and placebo. Approximately 400 subjects will be randomized into the study.
Treatment	LCZ696 (sacubitril and valsartan) plus placebo or valsartan plus placebo
Primary Objective and Endpoint	The proportional change from baseline in the AUC for NT-proBNP levels measured at 2, 4, 8, 12 and 24 weeks

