the subject should continue to take LCZ696 po BID until the randomization visit and site personnel should notify the CC. Subjects who fail the open-label run-in phase should receive a follow-up contact approximately 2 weeks after the last dose of study drug.

Doses will be assigned in the following fashion:

If previously taking no ACEI/ARB, low-dose ACEI/ARB[†], or eGFR < 30 ml/min/1.73m² ensure ACEI has been discontinued and the last dose of ACEI was ≥36 hours ago, then

- LCZ696 50 mg po plus placebo BID or valsartan 40 mg po BID plus placebo

If previously taking greater than low dose ARB[†]

- LCZ696 100 mg po plus placebo BID or valsartan 80 mg po BID plus placebo*

If previously taking greater than low dose ACEI[†], ensure ACEI has been discontinued and the last dose of ACEI was ≥ 36 hours ago, then

- LCZ696 100 mg po plus placebo BID or valsartan 80 mg po BID plus placebo*

† Low dose is defined as 24 hour dose of ≤ 10 mg lisinopril, ≤ 5 mg Ramipril, ≤ 50 mg Losartan, ≤ 10 mg Olmesartan, or other dose equivalent.

* At Investigator discretion, study drug may be started at the low dose (LCZ696/placebo 50 mg po BID or valsartan/placebo 40 mg po BID) if there are any concerns regarding tolerability at the 100 mg / 80 mg dose.)

Study drug will be supplied in kits (containing both active and placebo tablets) and will be administered as follows:

- 50 mg LCZ696 / 40 mg valsartan = one low-dose active tablet and one low-dose placebo tablet po BID
- 100 mg LCZ696 / 80 mg valsartan = one high-dose active tablet and one high-dose placebo tablet po BID
- 200 mg LCZ696 / 160 mg valsartan = two high-dose active tablets and two high-dose placebo tablets po BID

Assessments at this visit include:

- Interim history
- Review of medications
- Physical examination with NYHA class assessment
- Routine laboratory testing (creatinine, BUN, electrolytes – see visit 0 for labs to be collected)
- Core laboratory testing (Cystatin C, BNP, NT-proBNP)
- Adverse event monitoring

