Another secondary analysis of the AUC data for NT-proBNP will be conducted using a Wilcoxon nonparametric test with a worst-rank imputation based on the time-to-death. ⁹ A sample size of 190 subjects per group with available data will provide 80% power to detect the probability of 0.58 that an LCZ696 subject will have a better response than a valsartan subject. Similarly the sample size will provide 90% power to detect the probability of 0.60 that an LCZ696 subject will have a better response than a valsartan subject.

For the composite endpoint of all-cause mortality or first HF re-admission, we anticipate a 40% event rate at 24-weeks in the valsartan arm. The total sample size of 400 subjects will provide approximately 88% power to detect a difference of 40% vs. 25% for the LCZ696 arm. Similarly, there will be 55% power to detect a difference of 40% vs. 30%. The calculations were performed

using nQuery 7.0 and assume a 0.05 type I error rate (two-sided) with 1:1 randomization.

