18.3 Biomarker Core Laboratory

The University of Vermont will serve as the core laboratory for measurement of HFN biomarkers. Plasma specimens will be collected at Study Visits 2, 3, 4, 5, 7, and 10 (0, 2, 4, 8, 12, and 24 weeks from randomization), processed at the clinical centers according to the procedures provided by the core laboratory, and shipped to the core laboratory on dry ice (Refer to Biomarker Core Laboratory Manual of Procedures). Any subjects who agree to participate in the HFN biorepository sub-study will have samples collected at the clinical sites and stored at the University of Vermont biomarker core laboratory.

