## 9. Endpoint Descriptions

### 9.1 – Primary Endpoint

**Endpoint Description:** The log of the proportional change from baseline in the area under the curve for the ratio of NT Pro BNP compared to baseline, using the pre-COVID-19 population.

**Response Variable Definition:** All available time points will be used in the calculations. NT Pro BNP is measured at Baseline, Week 2, Week 4, Week 8, Week 12 and Week 24. The ratio of each of the post-Baseline measures will be calculated versus Baseline. The area under the entire piecewise dataset is the response variable. A visual example is provided showing a patients' hypothetical data for NT Pro BNP ratio to Baseline.

This area is determined by calculating the sum of the areas of each of the individual trapezoids. Each trapezoidal area is composed of the area bordered by the time interval on the x-axis (e.g., 0 to 2 Weeks), the respective NT Pro BNP ratio at each of the time points on the y-axis (e.g., 1 at x=0 and 0.7 at x=2), and the line segment connecting the NT Pro BNP ratios between the two y-axis values (1 and 0.7). The number of trapezoids available will depend on the completeness of the data.

It is expected that NT Pro BNP measurements may not be measured exactly at the specified time points. For example, the measurement corresponding to the 12 Week time point may actually be measured for example at 11 or 12.5 Weeks after randomization. In calculating the AUC, the measurement corresponding to Baseline will always be set at the 0 time point. Each post-Baseline visit will use the value for the visit timing, even if that timing is not exact (e.g., Week 12 visit will always assign a 12 for the x-axis). The final step in the calculation is to take log of the calculated area under the curve.

Additional Covariates in Addition to Randomized Treatment: Baseline log NT Pro BNP, atrial fibrillation status, random effect of patient

Handling of Dropouts and Missing Data: If missing NT Pro BNP at Week 24, use last observation carried forward (LOCF) from previous post-Baseline time point with available NT Pro BNP data. No adjustment will be made for missing Baseline results.

Sensitivity Analysis: Several sensitivity analyses will be performed.

- 1) Complete cases, using patients with available Baseline and Week 24 Week 24 NT Pro BNP data
- 2) For patients missing Week 24 value, impute 2.5xBaseline value for Week 24

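### The tertiary clinical-event models omit baseline log NT-proBNP, which the primary model already uses; adding it would gain a modest amount of power at almost no cost

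*SAP*

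**What the plan says.** **Event models.** SAP 11.1-11.5 use Cox models; for 11.4 the text is "The Cox regression model for survival data (PROC PHREG in SAS) will be used to test the statistical significance of differences". SAP 11.6 uses Poisson regression, and 11.7, 11.8 and 11.11 use logistic regression. In all nine sections the covariate entry is "Additional Covariates in Addition to Randomized Treatment: atrial fibrillation status at time of randomization". The only sensitivity analysis listed for each is a rerun in the original ITT population.

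**Primary model.** SAP 9.1 has "Additional Covariates in Addition to Randomized Treatment: Baseline log NT Pro BNP, atrial fibrillation status, random effect of patient". Protocol 16.4 also names log baseline NT-proBNP and atrial fibrillation (AF).

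**Availability.** Protocol 18.3: "Plasma specimens will be collected at Study Visits 2, 3, 4, 5, 7, and 10". Visit 2 is week 0, the randomisation visit (Protocol 12.1).

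**Stratification.** Site and AF status (Protocol 10.8 and 16.2; SAP 2.2). NT-proBNP is not a factor.

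**Protocol text on covariates for events.** Protocol 16.5 names AF for the key secondary regression and names no covariates for the Cox models.

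**Stated power.** Protocol 16.2, for death or first HF re-admission: "we anticipate a 40% event rate at 24-weeks in the valsartan arm", with "approximately 88% power to detect a difference of 40% vs. 25% for the LCZ696 arm" and 55% for 40% vs 30%, at 400 subjects.

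**The concern.** The protocol's hypothesis is that LCZ696 "will improve NT-proBNP levels, which reflect hemodynamic and clinical status". A plan that treats the marker as a reading of clinical status has reason to expect its baseline value to predict death and HF admission. In Cox and logistic models, leaving out a covariate that predicts the outcome pulls the estimated treatment effect toward the null, and power falls. Because NT-proBNP is not a stratification factor, the arms can also differ on it by chance, and the AF-only estimate then carries that difference.

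The attenuation argument does not carry over to the Poisson model in 11.6: a rate ratio is not pulled toward the null by omitting a balanced covariate. There the benefit is control of chance imbalance and less unexplained between-patient variation.

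At stake is some power on tertiary comparisons whose main analysis set is now 335 patients instead of the planned 400 (SAP 3).

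**Working it through.** **Step 1. Reproduce the stated power.** Inputs from Protocol 16.2: 200 per arm, two-sided 0.05, 40% vs 25% or 30%. Formula: power = Φ[(d − 1.96·se0)/se1], with se0 = √(2·p̄(1−p̄)/n) and se1 = √((p1(1−p1)+p2(1−p2))/n).

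- 40% vs 25%: se0 = 0.0468, se1 = 0.0462, power 89.6% (stated: about 88%).
- 40% vs 30%: se0 = 0.0477, se1 = 0.0474, power 55.5% (stated: 55%).

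Both reproduce. With 167.5 per arm (335 in total) the formula gives 83.7% and 48.3%, so the smaller analysis set costs about 6 and 7 points. That is separate from the covariate question.

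**Step 2. Simulate the planned and the adjusted Cox model.**

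- From the documents: 40% vs 25% or 30% at 24 weeks, 5% dropout (Protocol 16.2), N = 335 (SAP 3).
- Assumed, not in the documents: hazard ratio per 1 SD of baseline log NT-proBNP from 1.0 to 2.0; AF prevalence 35% with no effect on outcome.
- Model: event times are exponential with hazard exp(a + b·arm + g·x), where x is standard normal and g = ln(HR per SD). The values a and b are solved so that the event rates averaged over x equal the protocol's rates.
- Compared: treatment + AF against treatment + AF + x. There are 4,000 trials per cell, so each power has a standard error of at most √(0.25/4000) = 0.8 point. Both models are fitted to the same trials.

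Power at N = 335, AF only → AF + log NT-proBNP:

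| HR per SD | 40% vs 25% | 40% vs 30% |
|---|---|---|
| 1.0 | 83.1 → 83.1% | 47.7 → 47.4% |
| 1.3 | 83.5 → 84.2% | 47.1 → 47.9% |
| 1.5 | 83.2 → 85.9% | 48.5 → 51.6% |
| 1.75 | 82.4 → 86.6% | 47.5 → 52.8% |
| 2.0 | 83.1 → 89.1% | 47.5 → 55.7% |

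At N = 400 the gains run from 0.9 to 4.0 points (40% vs 25%) and from 0.9 to 7.7 points (40% vs 30%) over HR 1.3 to 2.0.

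**Step 3. Where the gain comes from.** At HR 2.0 per SD, 40% vs 30%, N = 335, the average estimated hazard ratio moves from 0.697 to 0.669, while its standard error is 0.190 and 0.191.

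- AF only: |ln 0.697|/0.190 = 1.90, and Φ(1.90 − 1.96) = 48%.
- Adjusted: |ln 0.669|/0.191 = 2.10, and Φ(2.10 − 1.96) = 56%.

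Both agree with the table. The gain is removal of attenuation, not a smaller standard error.

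**Step 4. Type I error (N = 335, 40% in both arms).** AF only 4.1-5.3%; adjusted 5.0-5.5%.

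**Step 5. Death alone.** The documents give no death rate. Assuming 15% vs 10% (3,000 trials): 27.6 → 27.8% at HR 1.5 and 27.7 → 29.7% at HR 2.0.

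**Step 6. Chance imbalance.** The arm difference in a standardised covariate has standard error √(4/335) = 0.109. A difference of 1.96 × 0.109 = 0.21 SD would shift the AF-only hazard ratio by roughly 1.5^0.21 = 1.09 to 2.0^0.21 = 1.16, that is 9-16%.

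**The case against.** The case for leaving the plan alone is substantial.

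- **Nothing is wrong with the planned test.** It holds its error rate, and the 88% and 55% come from an unadjusted calculation that the planned model matches. Chance imbalance is already part of the 5%. This stands.
- **The size is not documented.** No section gives the prognostic strength of baseline NT-proBNP. The Visit 2 sample also follows 3-7 days of open-label LCZ696, and the entry criterion accepts NT-proBNP or BNP up to three months old, so it says little about the Visit 2 value. This stands, and it is why the gain is shown as a range that includes no effect.
- **AF only is a recognisable choice.** AF is the non-site stratification factor, and the AUC models add the baseline of their own response. That explains the choice. It gives no reason to leave unused a prognostic baseline value that is already collected.
- **Changing the model is late.** 365 patients have been randomised and an interim efficacy analysis has been done (SAP 3 and 14). This limits the status the adjusted model can have, and the fix allows for it.

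The core point survives: at HR 1.0 power is essentially unchanged, and at every larger value it rises.

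**Conclusion.** The point holds as a modest, nearly free gain in efficiency for the regression models in SAP 11.1-11.8 and 11.11. For death or first HF hospitalisation at N = 335 the Cox gain is about 1 point at an assumed HR per SD of 1.3, 3 at 1.5, 4-5 at 1.75 and 6-8 at 2.0. It rests on that assumed range and on the protocol's event rates. The logistic and Poisson endpoints were not simulated.

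Four stronger readings are tempting, and the documents do not support them:

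- *The event analyses are invalid, or fall short of the stated power.* Type I error is near 5%, and the stated power reproduces at 400. The lower power at 335 comes from the smaller analysis set.
- *Power for mortality is materially lost.* For death alone the gain is about 0-2 points under the assumed rates.
- *Every event analysis adjusts for AF only.* The win ratio (SAP 12.1) has no covariates at all.
- *These are the trial's only mortality and HF-admission comparisons.* Secondary endpoint #1 (SAP 10.1) counts death, hospital days and a second HF admission, and the win ratio ranks death and HF admissions.

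**What to change.** Before unblinding, change the covariate line in SAP 11.1-11.8 and 11.11 to: *atrial fibrillation status at randomization and log baseline NT-proBNP*. Add three statements:

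- A patient without a baseline sample gets the mean log value plus a missing-value indicator, so that nobody leaves the analysis.
- The AF-only model is reported as supportive.
- The hazard or odds ratio is conditional on baseline NT-proBNP (table footnote).

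Protocol 16.1 requires analyses to be defined and approved before unblinding. The documents do not show whether the treatment codes have been opened for the final analysis. If they have, keep the AF-only model as the planned analysis and report the adjusted one as a labelled sensitivity analysis.

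The cost is one line in each of nine sections and no new data. The estimand does change, from an effect conditional on AF to one conditional on AF and baseline NT-proBNP. Protocol 16.5 names no covariates for the Cox models, so the SAP change does not conflict with it.
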